5.3.5.11 Adverse Events Associated with an Overdose

An overdose is the accidental or intentional use of a drug in an amount higher than the dose being studied. An overdose or incorrect administration of study treatment is not itself an adverse event, but it may result in an adverse event. All adverse events

associated with an overdose or incorrect administration of study drug should be recorded on the Adverse Event eCRF. If the associated adverse event fulfills serious criteria, the event should be reported to the Sponsor immediately (i.e., no more than 24 hours after learning of the event; see Section 5.4.2).

No safety data related to taselisib overdose is available.

5.3.5.12 Patient-Reported Outcome Data

Adverse event reports will not be derived from PRO data by the Sponsor, and safety analyses will not be performed using PRO data. However, if any PRO responses suggestive of a possible adverse event are identified during site review of the PRO data, the investigator will determine whether the criteria for an adverse event have been met and, if so, will report the event on the Adverse Event eCRF.

5.4 IMMEDIATE REPORTING REQUIREMENTS FROM INVESTIGATOR TO SPONSOR

Certain events require immediate reporting to allow the Sponsor to take appropriate measures to address potential new risks in a clinical trial. The investigator must report such events to the Sponsor immediately; under no circumstances should reporting take place more than 24 hours after the investigator learns of the event. The following is a list of events that the investigator must report to the Sponsor within 24 hours after learning of the event, regardless of relationship to study drug:

- Serious adverse events
- Non-serious adverse events of special interest
- Pregnancies

The investigator must report new significant follow-up information for these events to the Sponsor immediately (i.e., no more than 24 hours after becoming aware of the information). New significant information includes the following:

- New signs or symptoms or a change in the diagnosis
- Significant new diagnostic test results
- Change in causality based on new information
- Change in the event's outcome, including recovery
- Additional narrative information on the clinical course of the event

Investigators must also comply with local requirements for reporting serious adverse events to the local health authority and IRB/EC.

5.4.2 Reporting Requirements for Serious Adverse Events and Adverse Events of Special Interest

5.4.2.1 Events That Occur prior to Study Drug Initiation

After informed consent has been obtained but prior to initiation of study drug, only serious adverse events caused by a protocol-mandated intervention should be reported. A paper Serious Adverse Event Reporting Form and fax cover sheet should be completed and faxed to Roche Safety Risk Management or its designee immediately (i.e., no more than 24 hours after learning of the event), with use of the fax numbers provided to investigators (see "Protocol Administrative and Contact Information & List of Investigators").

5.4.2.2 Events That Occur after Study Drug Initiation

After initiation of study drug, serious adverse events and non-serious adverse events of special interest will be reported until 28 days after the last dose of study drug. Investigators should record all case details that can be gathered immediately (i.e., within 24 hours after learning of the event) on the Adverse Event eCRF and submit the report via the electronic data capture (EDC) system. A report will be generated and sent to Roche Safety Risk Management by the EDC system.

In the event that the EDC system is unavailable, a paper Serious Adverse Event/Adverse Event of Special Interest Reporting Form provided to investigators should be completed and submitted to the Sponsor or its designee immediately (i.e., no more than 24 hours after learning of the event), either by faxing or by scanning and emailing the form using the fax number or email address provided to investigators. Once the EDC system is available, all information will need to be entered and submitted via the EDC system.

Instructions for reporting post-study adverse events are provided in Section [5.6](#).

5.4.3 Reporting Requirements for Pregnancies

5.4.3.1 Pregnancies in Female Patients

Female patients of childbearing potential will be instructed to immediately inform the investigator if they become pregnant during the study or within 6 months after the last dose of fulvestrant. A Pregnancy Report eCRF should be completed by the investigator immediately (i.e., no more than 24 hours after learning of the pregnancy) and submitted via the EDC system. A pregnancy report will automatically be generated and sent to Roche Safety Risk Management. Pregnancy should not be recorded on the Adverse Event eCRF. The investigator should discontinue study drug and counsel the patient, discussing the risks of the pregnancy and the possible effects on the fetus. Monitoring of the patient should continue until conclusion of the pregnancy. Any serious adverse events associated with the pregnancy (e.g., an event in the fetus, an event in the mother during or after the pregnancy, or a congenital anomaly/birth defect in the child) should be reported on the Adverse Event eCRF.

In the event that the EDC system is unavailable, a paper Clinical Trial Pregnancy Reporting Form and fax cover sheet should be completed and faxed to Roche Safety Risk Management or its designee immediately (i.e., no more than 24 hours after learning of the pregnancy), using the fax numbers provided to investigators (see "Protocol Administrative and Contact Information & List of Investigators"). Once the EDC system is available, all information will need to be entered and submitted via the EDC system.

5.4.3.2 Abortions

Any abortion should be classified as a serious adverse event (as the Sponsor considers abortions to be medically significant), recorded on the Adverse Event eCRF, and reported to the Sponsor immediately (i.e., no more than 24 hours after learning of the event; see Section 5.4.2).

5.4.3.3 Congenital Anomalies/Birth Defects

Any congenital anomaly/birth defect in a child born to a female patient exposed to study drug should be classified as a serious adverse event, recorded on the Adverse Event eCRF, and reported to the Sponsor immediately (i.e., no more than 24 hours after learning of the event; see Section 5.4.2).

5.5 FOLLOW-UP OF PATIENTS AFTER ADVERSE EVENTS

5.5.1 Investigator Follow-Up

The investigator should follow each adverse event until the event has resolved to baseline grade or better, the event is assessed as stable by the investigator, the patient is lost to follow-up, the patient withdraws consent, *or the patient is no longer being followed for survival*. Every effort should be made to follow all serious adverse events considered to be related to study drug or trial-related procedures until a final outcome can be reported.

During the study period, resolution of adverse events (with dates) should be documented on the Adverse Event eCRF and in the patient's medical record to facilitate source data verification.

All pregnancies reported during the study should be followed until pregnancy outcome. If the EDC system is not available at the time of pregnancy outcome, follow reporting instructions provided in Section 5.4.3.1.

5.5.2 Sponsor Follow-Up

For serious adverse events, non-serious adverse events of special interest, and pregnancies, the Sponsor or a designee may follow up by telephone, fax, electronic mail, and/or a monitoring visit to obtain additional case details and outcome information (e.g., from hospital discharge summaries, consultant reports, autopsy reports) in order to perform an independent medical assessment of the reported case.

5.6 POST-STUDY ADVERSE EVENTS

The Sponsor should be notified if the investigator becomes aware of any serious adverse event that occur after the end of the adverse event reporting period (defined as 28 days after the last dose of study drug [see Section 5.3.1]), if the event is believed to be related to prior study drug treatment.

The investigator should report these events directly to Roche or its designee, either by faxing or by scanning and emailing the Serious Adverse Event/Adverse Event of Special Interest Reporting Form using the fax number or email address provided to investigators.

5.7 EXPEDITED REPORTING TO HEALTH AUTHORITIES, INVESTIGATORS, INSTITUTIONAL REVIEW BOARDS, AND ETHICS COMMITTEES

The Sponsor will promptly evaluate all serious adverse events and non-serious adverse events of special interest against cumulative product experience to identify and expeditiously communicate possible new safety findings to investigators, IRBs, ECs, and applicable health authorities based on applicable legislation.

To determine reporting requirements for single adverse event cases, the Sponsor will assess the expectedness of these events using the following reference document:

- Taselisib Investigator's Brochure
- Fulvestrant SmPC

The Sponsor will compare the severity of each event and the cumulative event frequency reported for the study with the severity and frequency reported in the applicable reference document.

Reporting requirements will also be based on the investigator's assessment of causality and seriousness, with allowance for upgrading by the Sponsor as needed.

Certain adverse events are anticipated to occur in the study population at some frequency independent of study drug exposure and will be excluded from expedited reporting. These anticipated events include, but are not limited to, the following:

- Nausea
- Vomiting
- Fatigue
- Injection-site pain
- Injection-site reaction
- Muscle pain
- Joint pain
- Tumor pain
- Hot flashes
- Weakness
- Loss of appetite
- Weight loss
- Worsening of general condition
- Failure to thrive

Until the primary PFS analysis has been completed, an iDMC will monitor the incidence of the above-listed anticipated events during the study. An aggregate report of any clinically relevant imbalances that do not favor the test product will be submitted to health authorities.

6. STATISTICAL CONSIDERATIONS AND ANALYSIS PLAN

6.1 DETERMINATION OF SAMPLE SIZE

The global study plans to enroll approximately 600 patients, including 480 patients with detectable *PIK3CA*-mutant tumors, and 120 patients without detectable *PIK3CA*-mutant tumors (tumor status determined by the cobas *PIK3CA* mutation test).

After the global enrollment closes, additional Chinese patients may continue to be recruited into the China extension cohort. A total of up to 150 patients with detectable *PIK3CA*-mutant tumors may be enrolled as part of the global study population and the China extension cohort combined (see Section 6.10 for further details).

The sample size of 480 patients with *PIK3CA*-mutant tumors is determined on the basis of the power calculation for the PFS and the OS endpoints, whichever requires a larger sample size. In this case, the sample size is driven by OS.

In 480 patients with *PIK3CA*-mutant tumors, approximately 287 investigator-assessed PFS events will be required to detect a hazard ratio of 0.59 in PFS (3.1 months of

improvement in median PFS) with 95% power at the a two-sided significance level of 1%, assuming a median PFS of 4.5 months in the control arm (Mauriac et al. 2009; Johnston et al. 2013). One interim efficacy analysis of investigator-assessed PFS will be conducted at 60% of PFS information (see Section 6.9.1 for more details). The α -spending function specified as Gamma (-16), which allocates two-sided $\alpha = 1.7 \times 10^{-5}$ at the interim efficacy analysis of investigator-assessed PFS, when 172 investigator-assessed PFS events have occurred. The minimal detectable difference for investigator-assessed PFS hazard ratio at final PFS analysis is 0.72 (i.e., 39% improvement in median investigator-assessed PFS from 4.5 months in the control arm compared with 6.2 months in the treatment arm), when 287 investigator-assessed PFS events have occurred.

With the aforementioned sample size of 480 patients with *PIK3CA*-mutant tumors, the OS analyses in this population will require 330 deaths to detect an hazard ratio of 0.7 in OS (11.1 months of improvement in median OS) with 80% power at a two-sided significance level of 5%, assuming a median OS of 26 months in the control arm based on the OS of 26.4 months in patients treated with 500 mg fulvestrant in the CONFIRM study, which investigated 500 mg fulvestrant versus 250 mg fulvestrant in a similar patient population (Di Leo et al. 2014).

The study plans to enroll 120 patients who do not have a detectable *PIK3CA*-mutant tumor, on the basis of the result of the cobas *PIK3CA* mutation test, to evaluate the clinical benefit in this population. If the observed hazard ratio in investigator-assessed PFS is 1 (no benefit), approximately 111 investigator-assessed PFS events will be observed at the analysis, and the 90% confidence interval will exclude a true hazard ratio < 0.72 (i.e., > 1.8 -month improvement in median PFS).

In total, approximately 400 patients will be treated with the combination of taselisib+fulvestrant in this study (320 patients with *PIK3CA*-mutant tumors and 80 patients without detectable *PIK3CA*-mutant tumors), which will enable the Sponsor to better characterize any rare but clinically significant safety events (e.g., for an adverse event with 4% frequency, there is 96% probability to observe ≥ 10 patients with such adverse event on the basis of 400 taselisib+fulvestrant-treated patients) to help enable the development of effective toxicity prevention and management guidelines for patients treated with the combination of taselisib and fulvestrant.

Assuming a 12-month site ramp-up period and a total of 200 sites, the enrollment duration will be driven by enrollment of patients with *PIK3CA*-mutant tumors and is projected to be approximately 28 months (from the first patient enrolled). The last PFS event (the 287th investigator-assessed PFS event) for the final PFS analysis in patients with *PIK3CA*-mutant tumors is projected to occur approximately 29 months after the first patient is enrolled.

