With the aforementioned sample size of 480 patients with *PIK3CA*-mutant tumors, the OS analyses in this population will require 330 deaths to detect a hazard ratio of 0.7 in OS (11.1 months of improvement in median OS) with 80% power at a two-sided significance level of 5%, assuming a median OS of 26 months in the control arm based on the OS of 26.4 months in patients treated with 500 mg fulvestrant in the CONFIRM study, which investigated 500 mg fulvestrant versus 250 mg fulvestrant in a similar patient population (Di Leo et al. 2014).

The study plans to enroll 120 patients who do not have a detectable *PIK3CA*-mutant tumor, on the basis of the result of the cobas *PIK3CA* mutation test, to evaluate the clinical benefit in this population. If the observed hazard ratio in investigator-assessed PFS is 1 (no benefit), approximately 111 investigator-assessed PFS events will be observed at the analysis, and the 90% confidence interval will exclude a true hazard ratio < 0.72 (i.e., > 1.8 -month improvement in median PFS).

In total, approximately 400 patients will be treated with the combination of taselisib + fulvestrant in this study (320 patients with *PIK3CA*-mutant tumors and 80 patients without detectable *PIK3CA*-mutant tumors), which will enable the Sponsor to better characterize any rare but clinically significant safety events (e.g., for an adverse event with 4% frequency, there is 96% probability to observe ≥ 10 patients with such adverse event on the basis of 400 taselisib + fulvestrant-treated patients) to help enable the development of effective toxicity prevention and management guidelines for patients treated with the combination of taselisib and fulvestrant.

Interim Analyses

The iDMC will convene to review cumulative safety data approximately every 6 months. Data on serious adverse events, death, and adverse events of special interest will be monitored by the iDMC approximately every 3 months.

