Three interim analyses for OS *were originally* planned in patients with *PIK3CA*-mutant tumors on the basis of the cobas *PIK3CA* mutation test. *As a result of the completion of the primary PFS analysis, the Sponsor has decided to limit the additional OS follow-up to one additional*

analysis. This additional OS analysis coincides with the originally planned second OS interim analysis.

The type I error is under strong control by using the Generalized Haybittle-Peto method.

No formal interim analysis is planned for the patients without detectable *PIK3CA* mutations.

The responsibility, membership, and communication flow of the iDMC are specified in the iDMC Charter.

LIST OF ABBREVIATIONS AND DEFINITION OF TERMS

Abbreviation	Definition
AI	aromatase inhibitor
AKT	protein kinase B
BICR	blinded independent central review
BRAF	murine sarcoma viral oncogene homolog B
AUC	area under the concentration–time curve
AUC _{0–24}	area under the concentration–time curve from 0 to 24 hours
AUC _{0–∞}	area under the concentration–time curve from Time 0 to infinity
CFDA	China Food and Drug Administration
CBR	clinical benefit rate
C _{max}	maximum observed plasma concentration
CR	complete response
CT	computed tomography
ctDNA	circulating-tumor DNA
CV	coefficient of variation
CYP3A4	cytochrome P450 3A4
DLT	dose-limiting toxicity
DOR	duration of response
EC	Ethics Committee
ECOG	Eastern Cooperative Oncology Group
eCRF	electronic Case Report Form
EDC	electronic data capture
EGFR	epidermal growth factor receptor
EORTC	European Organisation for Research and Treatment of Cancer
EQ-5D	EuroQol 5-Dimension Questionnaire
ER	estrogen receptor
FA	final analysis
FDA	(U.S.) Food and Drug Administration
FDG-PET	fluorodeoxyglucose positron emission tomography
FFPE	formalin-fixed paraffin-embedded
HbA1c	glycosylated hemoglobin
HBV	hepatitis B virus
HCV	hepatitis C virus
HER2	human epidermal receptor 2
HIPAA	Health Insurance Portability and Accountability Act

Abbreviation	Definition
HLA	human leukocyte antigen
HR	hazard ratio
HR+	hormone receptor positive
HRQoL	health-related quality of life
IA	interim analysis
ICH	International Conference on Harmonisation
iDMC	independent Data Monitoring Committee
IHC	immunohistochemistry
IM	intramuscular
IMP	investigational medicinal product
IND	Investigational New Drug (application)
IRB	Institutional Review Board
ISH	in situ hybridization
IxRS	interactive voice/Web response system
MAPK	mitogen-activated protein kinase
MBC	metastatic breast cancer

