3.2 END OF STUDY

The global study will be considered completed when the last patient, last visit (LPLV) *or safety follow-up with the last patient has occurred (28 days after the last dose of study drug), whichever occurs later*, or when the Sponsor decides to stop the study.

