4.5.11 Follow-Up Assessments

Until approximately the end of August 2018, patients who are discontinued from study treatment for reasons other than disease progression will be asked to continue to have tumor assessments performed and complete the PRO assessments approximately every 8 weeks (± 5 days) until disease progression.

Until approximately the end of August 2018, after study treatment discontinuation, patients will be followed for survival and subsequent anti-cancer therapies approximately every 3 months until death, loss to follow-up, withdrawal of consent, or study termination by the Sponsor.

Until approximately the end of August 2018, after experiencing disease progression, patients will also be asked to return to the clinic 4–6 weeks (for tumor and PRO assessments) and 12 weeks ± 7 days (for PRO assessments), even if a patient initiates anti-cancer therapy subsequent to study drug discontinuation.

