6.4.2.2 Overall Survival

The analyses for OS will be conducted in all randomized patients with *PIK3CA*-mutant tumors as a secondary endpoint of the study and will be tested on the basis of a hierarchical testing procedure to preserve type I error. That is, the OS analysis will be tested only if both investigator-assessed PFS and ORR have reached their respective significance levels. The overall type I error for OS is preserved at two-sided 5%.

OS will be analyzed with patients grouped according to the treatment arm assigned at randomization. Data for patients who are alive at the time of the analysis data cutoff will be censored at the last date they were known to be alive. Data from patients without post-baseline information will be censored at the date of randomization.

The analyses will be conducted using the stratified two-sided log-rank test, and the results from the unstratified log-rank test will also be provided. The OS curve for each treatment arm will be estimated by the Kaplan-Meier methodology, and the HR and its 95% CI will be estimated by the Cox proportional-hazards models.

Three interim analyses and one final analysis for OS *were originally* planned in patients with *PIK3CA*-mutant tumors on the basis of the results from the cobas *PIK3CA* mutation test (see [Table 12](#) and [Table 13](#)). *As a result of the completion of the primary PFS analysis, the Sponsor has decided to limit the additional OS follow-up to one additional analysis. This additional OS analysis coincides with the originally planned second OS interim analysis.*

1. The first interim OS analysis will be conducted at the time when both investigator-assessed PFS and ORR have reached their respective significance levels, so it could occur at the time of the interim efficacy or the final efficacy analysis for investigator-assessed PFS.
2. The second OS analysis will be conducted approximately 10 months after the first interim analysis.

Table 12 Analyses for OS if the First Interim OS Analysis Occurs at the Time of the Interim Efficacy Analysis of Investigator-Assessed PFS

	Estimated Timing (Clinical Data Cutoff)	OS Events	Two-Sided p-Value Boundary	Rejection HR Boundary ^a	Percentage Information
First OS IA	~21 months after FPI	~63	0.001	0.44	19%
Second OS analysis	~10 months after first OS IA	~134	0.010	0.65	41%

IA=interim analysis; FPI=first patient in; HR=hazard ratio; OS=overall survival; PFS=progression-free survival.

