^a Assuming exponential distributions for the OS event time of the two treatment arms.

Table 13 Analyses for OS if the First Interim OS Analysis Occurs at the Time of the Final Efficacy Analysis of Investigator-Assessed PFS

	Estimated Timing (Clinical Data Cutoff)	OS Events	Two-Sided p-Value Boundary	Rejection HR Boundary ^a	Percentage Information
First OS IA	~29 months after FPI	~118	0.001	0.53	36%
Second OS analysis	~10 months after first OS IA	~188	0.010	0.67	57%

IA=interim analysis; FPI=first patient in; HR=hazard ratio; PFS=progression-free survival.

^a Assuming exponential distributions for the OS event time of the two treatment arms.

The stopping boundaries are computed using the generalized Haybittle-Peto boundaries with unequal p-values being used in the α -spending function and will be adjusted on the basis of the actual number of OS events observed at each interim OS analysis.

The timing of the analyses are based on an assumption of an annual loss-to-follow-up rate of 5%. The study team will be unblinded at the time when the iDMC recommends to stop the study and the Sponsor decides to stop the study, or at the time of the final PFS analysis if the study is not stopped early. Investigators and patients will remain blinded to individual patient-level treatment assignment until *approximately the end of August 2018, at which time unblinding is permitted at the discretion of the investigator or Sponsor.*

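### Protocol v4 still states 80% power for OS at 330 deaths, but the two OS looks it keeps (about 118 and 188 deaths) give about 40% at the planned boundaries

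*Combined protocol and SAP*

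**What the plan says.** **Power statement.** Protocol v4 section 6.1 gives the OS basis for the sample size: the analyses "will require 330 deaths to detect an hazard ratio of 0.7 in OS (11.1 months of improvement in median OS) with 80% power", two-sided 5%, control median 26 months. The synopsis, under Determination of Sample Size, says the same: "will require 330 deaths to detect a hazard ratio of 0.7 in OS (11.1 months of improvement in median OS) with 80% power". These are the only OS power statements in the protocol.

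**Current OS plan.** Section 6.4.2.2 records that three interims and a final were originally planned, and that "the Sponsor has decided to limit the additional OS follow-up to one additional analysis". The synopsis (Interim Analyses) and section 6.9.1 add: "This additional OS analysis coincides with the originally planned second OS interim analysis". Table 13 therefore has two rows: about 118 deaths at p 0.001, and about 188 deaths at p 0.010 (57% information). The boundaries "will be adjusted on the basis of the actual number of OS events observed at each interim OS analysis".

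**Follow-up and end of study.** Section 4.5.11 reads: "Until approximately the end of August 2018, after study treatment discontinuation, patients will be followed for survival". Section 3.2 defines the end of the global study by the last visit or last safety follow-up, or by sponsor decision, with no reference to a number of deaths.

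**Gate.** Under section 6.4.2.2, "the OS analysis will be tested only if both investigator-assessed PFS and ORR have reached their respective significance levels".

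**SAP v2.** Signed in March 2017 and appending the version 3 synopsis, it still schedules a third OS interim and a final at about 330 deaths (sections 2.4, 4.4.2.2 with Tables 2 and 3, and 4.8).

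**The concern.** Version 4 marked the interim-analysis text as describing an original plan, but gave the power statement no such label. Section 6.1 still says in the future tense what the OS analyses will require, yet v4 plans no 330-death analysis. The looks that were removed are the ones that supplied about half of the stated power, and no passage gives the power of what is left.

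If PFS and ORR both succeed and OS is then tested without reaching significance, a reader who relies on section 6.1 would treat the result as fairly strong evidence against a hazard ratio of 0.7. With about 40% power it would be weak evidence.

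**Working it through.** **Inputs.** Allocation 2:1 (protocol 4.2). Design hazard ratio 0.7, control median 26 months (6.1). Looks at 118 and 188 deaths with two-sided p 0.001 and 0.010 (protocol Table 13). Dropped looks at 232 and 330 deaths with p 0.045 and 0.013 (SAP Table 3).

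**Which table applies.** The PFS p-value of 0.0037 in the v4 amendment rationale meets the final PFS boundary (0.01) but not the interim one (1.7×10⁻⁵). The first OS look can therefore only fall at the final PFS analysis, which is the Table 13 case.

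**Formulas.**
- Information at D deaths: I = D × (2/3) × (1/3) = 2D/9
- Mean of the test statistic at HR 0.7: 0.3567 × √I, since −ln 0.7 = 0.3567
- Hazard ratio at the boundary: exp(−z/√I)
- Correlation between looks i < j: √(Di/Dj)
- Cumulative power: one minus the multivariate normal probability of staying below every boundary so far

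**Original four-look plan.**

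| Deaths | √I | Mean at HR 0.7 | z | HR boundary (printed) | Cumulative power | Cumulative two-sided alpha |
|---|---|---|---|---|---|---|
| 118 | 5.121 | 1.826 | 3.291 | 0.526 (0.53) | 7.2% | 0.0010 |
| 188 | 6.464 | 2.305 | 2.576 | 0.671 (0.67) | 39.6% | 0.0104 |
| 232 | 7.180 | 2.561 | 2.005 | 0.756 (0.76) | 71.4% | 0.0463 |
| 330 | 8.563 | 3.054 | 2.484 | 0.748 (0.75) | 79.3% | 0.0500 |

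The computed boundaries match the printed ones, and total alpha comes to 5%. The median gain also reproduces: 26/0.7 − 26 = 11.1 months. A single look at 330 deaths at 5% would give Φ(3.054 − 1.960) = 86.3%, so the stated 80% fits the four-look plan (79.3%) and not a single final test.

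**Plan in v4.** Stopping after row two leaves 39.6%. A simulation with 2,000,000 draws also gives 39.6%. As a hand check, the 188-death look alone gives Φ(2.305 − 2.576) = 39.3%; the first look adds almost nothing.

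**Other true hazard ratios, two looks.** 58.5% at 0.65, 76.7% at 0.60, 79.9% at 0.59.

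**Shortfall in deaths.** 330 − 188 = 142, and 142/330 = 43%.

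**Sensitivity.**
- *Number of deaths.* The documents do not give the actual count. Over an assumed range, the last look alone at an unchanged p of 0.010 gives 35% at 170 deaths, 39% at 188 and 47% at 220.
- *Alpha.* If the 188-death look took all the alpha left from 5% (nominal p 0.0499), power would be 63.5%. Version 4 does not say that it will do this.

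**The case against.** The best defence is that section 6.1 explains why 480 patients were chosen, and for that purpose 80% is right. The rest of the section also keeps its planning tense after the PFS analysis, and nobody takes its enrolment projections as live forecasts. Version 4 openly discloses the dropped looks. Table 13 prints a rejection hazard ratio of 0.67, stricter than the design value of 0.70, so a careful reader can see that power at that look is below 50%. The 40% figure also depends on a projected death count and on boundaries that will be adjusted. Finally, SAP v2 predates v4 and could not have reflected it.

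Much of this stands. The 80% is out of date rather than miscalculated, the change of plan is not hidden, and 40% has to be tied to the planned boundaries. But the same amendment did label the other OS text as original, and seeing that power is under 50% is not the same as being told what it is. The rows needed to see where 80% came from are now only in the SAP. No reading restores 80%: even spending all the remaining alpha at 188 deaths gives 63.5%.

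On the SAP, its Background section says that it overrides the protocol's statistical section, while v4 ends survival follow-up around August 2018. Which plan governs cannot be settled from these documents, and the point about the protocol's power statement does not depend on it.

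**Conclusion.** The concern holds. Protocol v4 states a power for OS that its own OS plan does not provide: about 40% instead of 80% for a hazard ratio of 0.7, roughly half.

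The 40% assumes 2:1 allocation, proportional hazards, looks at 118 and 188 deaths, and the printed boundaries of 0.001 and 0.010. It also applies only if the OS test is reached; the documents do not report the ORR result. The effect is limited to how an OS result is read. OS is a gated secondary endpoint, and dropping later looks does not inflate type I error (the two remaining looks spend about 1.04% of the 5%). It should be corrected, but it does not threaten the primary analysis.

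**What to change.** 1. In protocol section 6.1 and in the synopsis (Determination of Sample Size), label 330 deaths and 80% power as the original four-look design, refer to section 6.4.2.2, and add: *Under the current plan OS is last analysed at a planned number of about 188 deaths. If the OS test is reached (PFS and ORR both significant), power for a hazard ratio of 0.7 is about 40% at the planned boundaries; boundaries will be adjusted to the actual number of deaths.*
2. If no later SAP already does so, reconcile SAP sections 2.3, 2.4, 4.4.2.2 (Tables 2 and 3) and 4.8 with the two OS looks in protocol v4.

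The cost is wording in two protocol places and the matching SAP sections, plus a less favourable stated power. Sample size, data collection, boundaries and type I error control do not change.
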